#### **5.1 ADVERSE EVENT (AE)**

According to the GCP (Clinical Trial Directive 2001/20/EC), an adverse event (AE) is defined as any untoward medical occurrence in a participant of the treated group during an experiment, and which does not necessarily have a causal relationship with this treatment. This definition includes physical signs, symptoms and laboratory test values. At study enrolment, laboratory values that fall outside the relevant reference range will not be reported as AEs.

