#### **4.4.4.5 Emergency unblinding**

No formal procedure will be established for the un-blinding of participants. None of the possible complications potentially related to the preservation method (e.g. discarding a kidney, primary non-function) require the absolute need for the participant to know the allocation arm in order to treat them in the best way. All adverse events will be collected and reported.

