All other reported SAEs will be reported to the DMC within 7 calendar days of notification, if appropriate. This will not include SAEs that may be expected as part of the risks of kidney transplant surgery. Adverse device events (SADEs, USADEs) and device deficiencies will also be reported to the device manufacturer. All SAEs will be followed up to resolution. The DMC will review the accumulating data at regular intervals.

SAE reporting will continue until completion of follow up at 1 year after transplantation. Participants transferred back for on-going care to referring centres will have their data including AEs related to the outcome measures collected by data collection forms sent to the participant's specialist. Participant cards will be provided to all participants of the study, with a contact telephone number (research nurse/ researcher) to inform regarding the occurrence of SAEs.

The Principle Investigator will also inform all investigators concerned and the device manufacturer of relevant information about USADEs that could adversely affect the safety of participants.

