#### **5.2 SERIOUS ADVERSE EVENT (SAE)**

An adverse event that results in:

- Death
- Life threatening condition
- Persistent significant disability or incapacity
- Prolongation of initial hospitalisation or re-hospitalisation
- Requiring intervention to prevent one of above
- Medical or surgical intervention to prevent life-threatening illness or injury or permanent impairment to a body structure or a body function.

Planned hospitalisation for a pre-existing condition, or a procedure required by the trial protocol, without serious deterioration in health, is not considered a SAE.

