## **5.9 CAUSALITY OF AN AE IN RELATION TO THE INTERVENTION**

- Highly probable: Apparent relationship in time between AE and intervention. Relationship between AE and intervention is already known or expected and there is an appropriate temporal relationship between therapy and AE.
- Probable: Known effect of the intervention with no possible other cause and appropriate temporal association.
- Possible: AE likely to be associated with the intervention and no other explanation for the AE, or known effect of intervention that could also be associated with another concomitant therapy, illness or external cause.
- Unlikely: Unlikely to be causally related; e.g. reaction occurred after intervention or is more likely to be due to another concomitant therapy, illness or external cause.
- Definitely not: AE known to be caused by another concomitant therapy, illness or external cause.
- Not assessable: Likelihood of AE not known, or relationship of AE to intervention, another concomitant therapy, illness or external cause is not clear. This category should be used very scarcely.

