#### **5.12 PROCEDURES FOR RECORDING ADVERSE EVENTS**

It is the responsibility of the local lead investigator to ensure that all adverse events (AEs, ADEs, and device deficiencies) occurring during the course of the study are recorded. This may include but not be limited to:

- A description of the event
- The dates of the onset and resolution
- Action taken
- Outcome
- Assessment of relatedness to the device
- Whether the AE is serious or not
- Whether the AE arises from device deficiency
- Whether the AE arises from user error

Adverse events that occur during the course of the study should be treated by established standards of care that will protect the life and health of the study subjects

It is the responsibility of the local lead investigator to collect all directly observed adverse events and all adverse events spontaneously reported by the participant. In addition each participant should be questioned about adverse events at each visit.

Adverse events that occur during the course of the study should be treated by established standards of care that will protect the life and health of the study participants

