### 5.13 Surgical Complications Classification (within 30 days of transplantation)

The Clavien-Dindo classification (19) will be used to rank surgical complications according to an objective, simple, reliable and reproducible way. This classification is based on the type of therapy required to treat the complication.

**Table 1:** Clavien-Dindo Classification of Surgical Complications

Grades	Definition
Grade I	Any deviation from the normal postoperative course without the need for pharmacological treatment or surgical, endoscopic and radiological interventions. Acceptable therapeutic regimens are: drugs as anti-emetics, antipyretics, analgesics, diuretics and electrolytes, and physiotherapy. This grade also includes wound infections opened at the bedside.
Grade II	Requiring pharmacological treatment with drugs other than such allowed for grade I complication. Blood transfusions and total parenteral nutrition are also included.
Grade III	Requiring surgical, endoscopic or radiological intervention.
Grade III-a	Intervention not under general anaesthesia.
Grade III-b	Intervention under general anaesthesia.
Grade IV	Life-threatening complication (including CNS complications) requiring intensive care treatment.
Grade IV-a	Single organ dysfunction (including dialysis).

Grade IV-b	Multi-organ dysfunction.
Grade V	Death of patient.
Suffix “d”	If the patient suffers from a complication at the time of discharge, the suffix “d” (for disability) is added to the respective grade of complication. This label indicates the need for a follow-up to fully evaluate the complication.

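### The adverse event definition names only the treated group, against the protocol's own all-participant collection rules, and the timing example for an Unlikely causal link fits every event after implantation

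*Protocol*

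**What the plan says.** Section 5.1 defines an adverse event as "any untoward medical occurrence in a participant of the treated group during an experiment", whether or not it is caused by the treatment. Section 5.2 defines a serious adverse event as a subset of these: "An adverse event that results in" death, a life-threatening condition or one of the other listed outcomes.

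The collection rules are worded more widely:

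- Section 4.4.4.5: "All adverse events will be collected and reported".
- Section 5.12 makes it the local lead investigator's duty "to ensure that all adverse events (AEs, ADEs, and device deficiencies) occurring during the course of the study are recorded", and adds: "In addition each participant should be questioned about adverse events at each visit".
- Section 5, on notifying serious events: "Participant cards will be provided to all participants of the study".
- Section 5.13, for the first 30 days: "The Clavien-Dindo classification (19) will be used to rank surgical complications", with no limit by arm.

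Section 5.9 grades causality. The Unlikely grade reads in part: "Unlikely to be causally related; e.g. reaction occurred after intervention". In the same list, Highly probable and Probable both require the event's timing to fit the intervention.

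**The concern.** There are two separate wording faults in definitions that site staff apply case by case.

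The first is who can have an adverse event. The recording rules use the defined term, so a site that turns to the definition finds that it names one group only. Under Section 4.4.4.4 care providers know the allocation. Staff who know the arm and read Section 5.1 literally could record control-arm events less fully. Section 5.11 lists infection, fluid collection, lymphocele and cardiac or respiratory failure as anticipated, yet requires reporting when their frequency or severity exceeds expectation. The control arm is the natural benchmark for that judgement within the trial. Serious events expected from transplant surgery are also left out of the 7-day reports to the data monitoring committee (DMC) under Section 5, so those reports would not reveal a gap.

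The second is how relatedness is graded. If coming after the intervention is offered as a sign that a link is unlikely, an assessor is nudged away from attributing events to the device. Section 5.9 is the only causality scale in the protocol, and Section 5.12 asks for device relatedness without offering another. Whether an event counts as an adverse device effect (Section 5.3), and so goes to the manufacturer (Section 5), depends on that judgement.

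**Working it through.** No figure is in dispute, so the check is a comparison of the sections.

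**A. Who is covered**

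1. Elsewhere the protocol contrasts intervention with control (Section 6.1) and heads the arms as the machine perfusion study group (4.5.1) and the static cold storage control group (4.5.2). On that usage, the treated group in Section 5.1 most naturally means the perfusion arm.
2. Section 5.2 starts from the adverse event, so the same limit passes to serious events and to the 24-hour reporting duty in Section 5.
3. Sections 4.4.4.5 and 5.12 refer to all adverse events. Section 5.12 also has each participant questioned, and Section 5 gives every participant a card. None is limited by arm.
4. Steps 2 and 3 cannot both be followed to the letter. If the definition governs, questioning control participants yields nothing recordable. If the collection rules govern, the definition is wrong.
5. Outer bound of the literal reading: the whole control arm, 131 of 262, or 131/262 = 50%. This is the size of the arm, not an estimate of events lost.

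**B. The causality example**

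1. Section 4.5.1 keeps the kidney on the pump until the recipient's vessels are ready. Perfusion is therefore over before the kidney is implanted.
2. Perfusion acts on the kidney outside the body. Any effect on the recipient must follow implantation, and so must follow the intervention.
3. Every event that could be a true device effect in a recipient therefore meets the example given for Unlikely. An example that fits all candidate events cannot separate likely from unlikely ones.
4. Highly probable and Probable ask for suitable timing. For a treatment given before implantation, suitable timing means onset afterwards. One observation, onset after perfusion, thus counts towards the two highest grades and also illustrates a low one.

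**C. What does not depend on either definition**

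Graft survival, recipient survival, dialysis and serum creatinine are scheduled for all recipients (Appendix B). Delayed graft function, primary non-function and biopsy-proven rejection are secondary outcomes compared between the arms (Section 4.2.2). These are captured as endpoints whatever Section 5.1 says. What is exposed is the remainder: adverse events that are not endpoints.

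**The case against.** A reader might infer that no adverse event can be recorded under cold storage, so that safety cannot be compared between the arms. The protocol does not support this. Sections 4.4.4.5, 5, 5.12 and 5.13 all point to collection in both arms, and Section 5.14 repeats the participant cards and the data collection from referring centres without limit by arm. The main harms are endpoints in both arms. The term may also be loose, since Section 6.2 calls each arm a treatment arm, and nothing in Section 5 tells sites not to enter control events. This part of the objection stands. What remains is a contradiction that sites may resolve in different ways.

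A reader might also infer that the scale forces every later event into Unlikely and that device effects will be under-classified. That goes too far as well. The wording is one example, the higher grades stay available, and Section 5.3 defines a device effect without reference to the scale. Serious events and device deficiencies must be reported within 24 hours whatever the causality (Section 5), and those judged an immediate risk go to the DMC, manufacturer and ethics committees with no relatedness condition. This also stands. The example can mislead an assessor, but it does not bind one.

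Neither answer removes the faults. The wider collection rules contradict the definition without repairing it, and an example that fits every candidate event has no use in a grading scale.

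**Conclusion.** Both faults are in the text and should be corrected.

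- **Definition.** Sections 5.1 and 5.2 conflict with Sections 4.4.4.5, 5 and 5.12. The consequence is a risk of uneven recording of non-endpoint adverse events. It assumes that some unblinded staff would apply Section 5.1 literally, which is plausible but not shown.
- **Causality example.** It contradicts the timing criteria of Probable and Highly probable and fits every event after implantation. It could bias relatedness ratings downward. How far depends on how much weight assessors give to an example.

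The protocol offers no basis for a number of events missed or misgraded; the 50% above is only the limit of a literal reading. The primary endpoint, its analysis and the sample size are unaffected.

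**What to change.** 1. **Section 5.1:** replace the reference to the treated group with participants in either randomised group, in line with Section 5.12. Section 5.2 then needs no change. Wording by randomised group also covers kidneys allocated to perfusion but kept on ice, which Section 6.7 retains in the perfusion arm.
2. **Section 5.9:** under Unlikely, replace the example with timing that is not compatible with the intervention, such as onset before it, so that all grades use timing in the same direction.

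The cost is two sentences and matching guidance for the electronic case report form. Section 5.12 already asks for these events from each participant, so no new assessment is needed. Section 9.3 requires an approved written amendment for any protocol change, so the edits could go into the next one. How events are tabulated by arm is for the SAP or the DMC charter and is not part of this point.

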#### **5.2 SERIOUS ADVERSE EVENT (SAE)**

An adverse event that results in:

- Death
- Life threatening condition
- Persistent significant disability or incapacity
- Prolongation of initial hospitalisation or re-hospitalisation
- Requiring intervention to prevent one of above
- Medical or surgical intervention to prevent life-threatening illness or injury or permanent impairment to a body structure or a body function.

Planned hospitalisation for a pre-existing condition, or a procedure required by the trial protocol, without serious deterioration in health, is not considered a SAE.

### **5.3 ADVERSE DEVICE EFFECT (ADE)**

An adverse event related to the use of an investigational medical device. This definition includes any events resulting from insufficient or inadequate instructions for use, deployment, implantation, installation, or operation, or any malfunction of the investigational device. This definition also includes any event resulting from user error or from intentional misuse of the investigational device.

### **5.4 SERIOUS ADVERSE DEVICE EFFECT (SADE)**

Adverse device effect that has resulted in any of the consequences characteristic of a serious adverse event.

### **5.5 ANTICIPATED SERIOUS ADVERSE DEVICE EFFECT (ASADE)**

An effect which by its nature, incidence, severity or outcome has been identified as a risk associated with the procedure.

### **5.6 UNANTICIPATED SERIOUS ADVERSE DEVICE EFFECT (USADE)**

Serious adverse device effect which by its nature, incidence, severity or outcome has not been identified in the current version of the risk report.

### **5.7 DEVICE DEFICIENCY**

Inadequacy of a medical device with respect to its identity, quality, durability, reliability, safety or performance. Device deficiencies include malfunctions, use errors and inadequate labelling.

Device deficiencies that did not lead to an adverse event, but could have led to a medical occurrence if suitable action had not been taken, or intervention had not been made or if circumstances had been less fortunate will also be managed as detailed.

### **5.8 USE ERROR**

Act or omission of an act that results in a different medical device response than intended by the manufacturer or expected by the user. Use error includes slips, lapses and mistakes. An unexpected physiological response of the participant does not itself constitute a use error.

## **5.9 CAUSALITY OF AN AE IN RELATION TO THE INTERVENTION**

- Highly probable: Apparent relationship in time between AE and intervention. Relationship between AE and intervention is already known or expected and there is an appropriate temporal relationship between therapy and AE.
- Probable: Known effect of the intervention with no possible other cause and appropriate temporal association.
- Possible: AE likely to be associated with the intervention and no other explanation for the AE, or known effect of intervention that could also be associated with another concomitant therapy, illness or external cause.
- Unlikely: Unlikely to be causally related; e.g. reaction occurred after intervention or is more likely to be due to another concomitant therapy, illness or external cause.
- Definitely not: AE known to be caused by another concomitant therapy, illness or external cause.
- Not assessable: Likelihood of AE not known, or relationship of AE to intervention, another concomitant therapy, illness or external cause is not clear. This category should be used very scarcely.

## **5.10 GRADE OF SEVERITY**

- Mild (grade 1): participant is aware of symptoms but tolerates them easily. Symptoms do not interfere with daily activity.
- Moderate (grade 2): participant experiences discomfort that interferes with normal activity. No treatment is required except acetaminophen.
- Severe (grade 3): participant is unable to carry out normal activity. Treatment is required.
- Life-threatening (grade 4): emergency room visit or disabling or hospitalization.

## **5.11 ANTICIPATED ADVERSE EVENTS**

### General

- Infection (chest, urine, blood, wound, abdominal)
- Cardiac failure
- Respiratory failure

### Events related to the disease / condition /surgery

- Fluid collection (around transplanted kidney)
- Lymphocele
- Rejection
- Delayed graft function
- Primary non function
- Graft loss
- Admission for suspected rejection
- Occurrence and treatment of abdominal or wound infection
- Respiratory failure requiring appropriate treatment
- Hospitalisation for pre-existing condition that has not deteriorated
- Clinically significant abnormal laboratory finding or other abnormal assessments that is associated with the disease being studied (unless judged by the investigator as more severe than expected for the participant's condition)

The investigator will exercise his/her medical judgment in deciding whether an abnormal laboratory finding or other abnormal assessment is clinically significant. However, if in the opinion of the investigator, the frequency or severity of the event is greater than would be expected then it must be reported.

#### **5.12 PROCEDURES FOR RECORDING ADVERSE EVENTS**

It is the responsibility of the local lead investigator to ensure that all adverse events (AEs, ADEs, and device deficiencies) occurring during the course of the study are recorded. This may include but not be limited to:

- A description of the event
- The dates of the onset and resolution
- Action taken
- Outcome
- Assessment of relatedness to the device
- Whether the AE is serious or not
- Whether the AE arises from device deficiency
- Whether the AE arises from user error

Adverse events that occur during the course of the study should be treated by established standards of care that will protect the life and health of the study subjects

It is the responsibility of the local lead investigator to collect all directly observed adverse events and all adverse events spontaneously reported by the participant. In addition each participant should be questioned about adverse events at each visit.

Adverse events that occur during the course of the study should be treated by established standards of care that will protect the life and health of the study participants

### 5.13 Surgical Complications Classification (within 30 days of transplantation)

The Clavien-Dindo classification (19) will be used to rank surgical complications according to an objective, simple, reliable and reproducible way. This classification is based on the type of therapy required to treat the complication.

**Table 1:** Clavien-Dindo Classification of Surgical Complications

Grades	Definition
Grade I	Any deviation from the normal postoperative course without the need for pharmacological treatment or surgical, endoscopic and radiological interventions. Acceptable therapeutic regimens are: drugs as anti-emetics, antipyretics, analgesics, diuretics and electrolytes, and physiotherapy. This grade also includes wound infections opened at the bedside.
Grade II	Requiring pharmacological treatment with drugs other than such allowed for grade I complication. Blood transfusions and total parenteral nutrition are also included.
Grade III	Requiring surgical, endoscopic or radiological intervention.
Grade III-a	Intervention not under general anaesthesia.
Grade III-b	Intervention under general anaesthesia.
Grade IV	Life-threatening complication (including CNS complications) requiring intensive care treatment.
Grade IV-a	Single organ dysfunction (including dialysis).

Grade IV-b	Multi-organ dysfunction.
Grade V	Death of patient.
Suffix “d”	If the patient suffers from a complication at the time of discharge, the suffix “d” (for disability) is added to the respective grade of complication. This label indicates the need for a follow-up to fully evaluate the complication.

#### 5.14 STUDY SUSPENSION OR EARLY TERMINATION

The DMC or sponsor may recommend suspension or termination of the study either at an individual investigation site or the entire study for significant and documented reasons. An investigator, ethics committee or regulatory authority may suspend or prematurely terminate participation in the study at the investigation sites for which they are responsible. If suspicion of an unacceptable risk to subjects arises during the study, or when so instructed by the ethics committee or regulatory authorities, the sponsor shall suspend the study while the risk is assessed. The sponsor shall terminate the study if an unacceptable risk is confirmed.

The sponsor shall consider terminating or suspending the participation of a particular study site or investigator in the study if monitoring or auditing identifies serious or repeated deviations on the part of an investigator.

If suspension or premature termination occurs, the terminating party shall justify its decision in writing and promptly inform the other parties with whom they are in direct communication. The principal investigator and sponsor shall keep each other informed of any communication received from either the ethics committee or the regulatory authority.

If, for any reason, the sponsor suspends or prematurely terminates the study at an individual investigation site, the sponsor shall inform the responsible regulatory authority as appropriate and ensure that the Ethics Committee is notified, either by the principal investigator or by the sponsor. If the suspension or premature termination was in the interest of safety, the sponsor shall inform all other investigators.

If suspension or premature termination occurs,

- a) the sponsor shall remain responsible for providing resources to fulfil the obligations from the study protocol and existing agreements for following up the subjects enrolled in the study, and

- b) the principal investigator or authorized designee shall promptly inform the enrolled subjects at his/her study site, if appropriate.

Device deficiencies and use errors not falling into the categories of ADEs or SADEs should be reported via the online data collection tool and will be collected by the study investigators for investigation by the manufacturer.

SAE reporting will continue until the last patient recruited has completed 12 months of follow-up. Patients transferred back for on-going care to referring centres will have their data including AEs related to the outcome measures collected by data collection forms sent to the patient's specialist. Patient cards will be provided to all participants of the study, with a contact telephone number (research nurse / researcher) to inform regarding the occurrence of SAEs.

